In our day to day clinical practice we have encountered many of them with neurological complaints mimicking thiamine deficiency (TD). Investigations to confirm this condition are not available in our setting. So, the diagnosis of TD in such contexts is a real challenge and a high level of clinical suspicion should be demonstrated in such situations. Early treatment with thiamine has the potential to rapidly reverse clinical signs and minimize sequelae, before the onset of fixed lesions. The lack of diagnostic capacity in our settings justifies the use of a therapeutic thiamine challenge in cases with high clinical suspicion. However, there is paucity of study about the clinical spectrum and therapeutic response of such patients in Bangladesh. The aim of this prospective hospital based quasi-experimental study will be to determine the clinical pattern of patients with suspected dry beriberi and their outcome to thiamine therapeutic challenge in our setting. Fifty-five patients of clinically suspected dry beriberi will be enrolled as per inclusion and exclusion criteria. Then therapeutic trial of Inj. Thiamine will be given IV for 1st week (200mg IV daily for peripheral neuropathy and then orally (tab. Thiamin 100mg bd) for 11 weeks. Patients will be followed up after 1, 6 and 12 week to see the response. Pre and post treatment data will be recorded in pre designed case record form. To determine whether any of the difference between pretreatment and post treatment values were statistically significant or not, either Friedman's test or Cochran's Q test were used. Former test compares the quantitative variables and non-dichotomous qualitative variables and the later test compares the dichotomous qualitative/categorical variables. Statistical significance were defined as $P < 0.05$ and confidence interval was set at 95% level. Analysis will be performed with SPSS version 23. Our study result is likely to sensitize the health professionals of this region about this neglected health issue by increasing awareness of the clinical spectrum of Thiamine Deficiency related Peripheral Neuropathy. Moreover, study may provide the impetus for fashioning national policies on the diagnosis, treatment and prevention of thiamine deficiency disorders in our country.

Part-D

1. Introduction:

According to World Health Organization (WHO) International Nomenclature of Diseases, Thiamine deficiency (TD) syndrome is a clinical syndrome that arises insidiously as a result of a severe, prolonged deficiency of thiamine in the diet, manifested in the initial stages by anorexia, malaise, and weakness of the legs, frequently with paraesthesia; there may be slight oedema and palpitations. The disorder may persist in this chronic state or may at any time progress to an acute condition characterized either by cardiac involvement with oedema or by peripheral neuropathy; forms intermediate between these two extremes may also occur. It is thought that the basic cause is the inhibition of a series of enzyme-catalysed cleavages of carbon-carbon bonds in which thiamine diphosphate is a coenzyme. Commonly used synonyms are beriberi; Ceylon sickness; occidental beriberi (in part); oriental beriberi (in part); rice disease etc. The disorder (or spectrum of disorders) is classically associated with a diet consisting largely of polished rice (oriental beriberi), but may also arise if highly refined wheat flour forms a major part of the diet, in alcoholics, and in food faddists (occidental beriberi).¹

Thiamin (vitamin B1) is widely distributed in foods of both vegetable and animal origin. It is an essential micronutrient with dual coenzymatic and non-coenzymatic functions. It is involved in carbohydrate and branched-chain amino acid metabolism, as well as in the production of neurotransmitters, myelin, and nucleic acids. There is also evidence that thiamine plays a role in immune and anti-inflammatory processes and gene regulation.²⁻⁵

The human body requirement for thiamine is exclusively dependent on regular dietary intake, as there is no significant mechanism for endogenous production of thiamine or for prolonged storage of thiamine in the human body. It is estimated that the body can store thiamine for 2–3 weeks. Staple diets that are deficient in thiamine would result in low body thiamine levels, which may be subclinical or may manifest as a thiamine-deficiency syndrome. Thiamine deficiency is classically associated with diets consisting mainly of

milled white cereals, particularly polished rice and highly refined wheat flour. Milling significantly reduces the thiamine content of cereals: the thiamine content of highly milled white rice is 0.08 mg/100 g compared with 0.33 mg in unmilled brown rice. Rice washing and cooking methods may result in additional losses of up to 45–60% of thiamine. Rice is the most important food source in our country. The combination of limited body storage and a high turnover rate (half-life <10 days) results in potential depletion of thiamine stores within 2 weeks if it is not continuously replaced. In addition, thiamine's hydrosolubility, coupled with its renal clearance profile, contributes to a propensity to thiamine deficiency (TD) throughout life.^{1,6}

It principally affects precarious communities where children and adults are most vulnerable and where dietary habits rely on refined processed cereals or tubers (e.g., rice, wheat, cassava), notably in Southeast Asia and Africa. TD can result from various mechanisms that are not mutually exclusive. The most frequent mechanisms are insufficiency of dietary thiamine (enteral–parenteral supply) and poor intestinal absorptive capacity during malnutrition, tropical enteropathy, or secondary to surgical resection of large portions of the gastrointestinal tract. A relative inadequacy of thiamine content to caloric ratio (high carbohydrate diets) is also common. It is this thiamine–calorie imbalance that is responsible for TD in heavy drinkers of sweet drinks and contributes to the onset of TD when dextrose-based fluids are administered without thiamine supplementation in critically ill patients. Poor thiamine intake may be due to losses from food secondary to pre-cooking and food processing (e.g., repetitive rice washing), a restrictive diet due to cultural habits and ingestion of antithiamine factors (tea leaves, betel nuts, and coffee) or thiaminases (e.g., fermented raw fish, mycotoxins, stored food, and larvae) that break down and, thus, inactivate thiamine. Excessive loss of thiamine from the body, such as renal (loop diuretics, osmotic diabetic diuresis) or digestive losses (chronic diarrhea, hyperemesis), can also precipitate TD. At cellular level, two main mechanisms contribute to TD – impaired uptake or increased demand. Impaired cellular uptake of thiamine can be due to defects in thiamine transporters or specific enzymes (mutation, hypomagnesemia, drug-induced interaction), or reduced

levels of ThDP. Increased cellular demand of thiamine occurs in hypermetabolic states during critical illness, e.g., severe infections, shock, burns, fever, hyperthyroidism. Exposure to toxic substances, such as alcohol can also affect thiamine metabolism. When this occurs during pregnancy, the fetus may be indirectly affected, as observed in fetal alcohol syndrome. Maternal TD associated with excessive alcohol consumption is usually secondary to inadequate thiamine intake or decreased intestinal absorption due to reduced expression of ThTr-1. In addition, impaired intracellular thiamine utilization affecting the TPK activity results in a low bioavailability of the active cellular ThDP due to ethanol and acetaldehyde exposure. In humanitarian fields, TD occurring in epidemic proportions has been described following abrupt food shortage caused by disasters, famines, conflicts, or large population displacement.⁷

TD in adult may be manifested in three forms: TD with peripheral neuropathy, TD with cardiomyopathy and TD with lactic acidosis. TD with peripheral neuropathy is an acute form of thiamine deficiency characterized by polyneuropathy with paraesthesia of the extremities (especially the legs), reduced knee jerk and other tendon reflexes, and progressive severe weakness and wasting of muscles; the susceptibility to infections is greatly increased. Synonyms are atrophic beriberi; dietetic neuritis (in part); dry beriberi; endemic polyneuritis; panneuritis endemica; paralytic beriberi; polyneuritis endemica. The neurological signs constitute dry beriberi are evident even in the early stages. Polyneuritis and paralysis of the peripheral nerve predominate; the central nervous system is scarcely involved. Manifestations are seen in the autonomic, sensory and motor systems. The autonomic nervous system is functionally altered in the early course of disease, as the clinical and pharmacological findings in beriberi patients suggest. In the sensory system, tactile sensation is the first affected, then there is pain, and finally temperature sensitivity altered. The sensory disturbances are usually not so marked as to be termed 'anesthesia', but superficial hyperesthesia is more or less characteristically distributed, beginning in the lower extremities, finger tips, lower abdomen and perioral

areas and gradually expanding. The sensory effects are usually symmetrical although the side that is greater use tends to be affected first. Paraesthesia is often the earliest sign of diminished sensitivity and the patients complains of burning sensation in the legs and toes. Although rare, sensory disturbances of the oral cavity are encountered in a few cases. Paralysis of the motor nerves occurs after the sensory disturbances. This also begins in the tips of the lower extremities, then in the fingers, and ascends progressively. There is increasing muscular weakness which is readily demonstrated by the inability of the individual to rise from a squatting position without assistance and, as the disease progresses, there is atrophy of the leg muscles. The tendon reflexes are also affected especially with loss of ankle and knee jerks. Painful calf muscles and, eventually, foot drop and, later, wrist drop may also develop. Advanced neurological changes may result in great difficulty in walking and may even lead to complete paralysis. Frequently, vertigo and instability of the body during walking are noted in beriberi patients. The shaky gait is equivalent to positive Romberg's sign and mostly caused by impaired vestibular function in advanced cases although it is partially due to decrease deep sensations. Nystagmus, as a sign of manifestation of vestibular malfunction, has been reported to occur particularly in alcoholics who developed Wernick's encephalopathy.^{1,6}

Epidemics of beriberi manifesting with sensory neuropathy and gait ataxia have been described in children and adults within segments of the African population subsisting on diets that provide marginal or submarginal intakes of thiamine⁸ in prison populations^{9,10} and in garrisoned troops.¹¹ Seasonal ataxic syndrome is an acute thiamine deficiency state that has occurred in epidemics in parts of Western Nigeria during the rainy season and manifested with clinical features of Wernicke's encephalopathy. Studies have confirmed that seasonal ataxic syndrome is a thiamine-deficiency disorder that occurs in low-income individuals with marginal thiamine deficiency. Tropical ataxic neuropathy (TAN) is a syndrome of sensory polyneuropathy, sensory ataxia, bilateral optic atrophy, and bilateral sensorineural deafness described in several African countries. The cardinal clinical features of TAN are similar to those of thiamine deficiency.¹² A therapeutic trial of thiamine in these patients has indicated that it is a thiamine deficiency state.¹³

Besides there are some clinical conditions which may probably be results from TD. There are some neurologic syndromes of undetermined etiology occurring in parts of Africa that are probable thiamine-deficiency syndromes but have not been conclusively investigated and confirmed to be due to thiamine deficiency. One of these is epidemic spastic paraparesis (konzo), a severely debilitating disorder characterized by abrupt onset of paraplegia occurring in patients subsisting almost exclusively on a diet of improperly processed cassava roots.¹⁴ Epidemics have been reported from several countries in Central and East Africa affecting hundreds of thousands of people, predominantly children and young women. The etiology remains unknown, but several aspects of the clinical presentation are suggestive of a thiamine-deficiency disorder.¹² Thiamine levels have never been tested in these patients, and a therapeutic trial of thiamine has never been performed. Another probable thiamine-deficiency disorder is the epidemic optic neuropathy associated with peripheral neuropathy, which has been reported in Tanzania and Somalia.^{15,16} The clinical description of the syndrome is quite similar to the epidemic of optic and peripheral neuropathy described in Cuba, where patients were found to be thiamine deficient and responded to vitamin B supplementation.¹⁷ The epidemic optic neuropathy syndrome may well be a forme fruste of TAN, which also presents with optic neuropathy and peripheral neuropathy. Although acute cases of epidemic optic neuropathy have been successfully treated with vitamin B supplementation in Tanzania,¹⁶ thiamine levels have never been tested in these patients, and a therapeutic trial of thiamine has never been conducted.

Thiamine deficiency can be investigated using plasma, erythrocytes, whole blood ThPP levels and urinary excretion of thiamine before and after exogenous thiamine administration.¹⁸ However, serum or whole blood thiamine has poor sensitivity and specificity in severe acute conditions as it decreases during systemic inflammation, and represents only a small part of the whole body thiamine pool. Erythrocyte transketolase activity more accurately evaluates the thiamine status of the body and is, therefore, used

as standard.¹⁹ MR imaging showing specific lesions can also be very helpful in early detection of neurologic features of TD in children. However, none of these investigations allow immediate diagnosis of TD in life-threatening conditions and they are rarely available in resource-limited settings. Consequently, the diagnosis of TD in such contexts is a real challenge, especially considering its wide and non-specific clinical spectrum and potentially fatal prognosis. A high level of clinical suspicion should be demonstrated in the following situations: suspicion of infantile beriberi; unexplained neurological signs, encephalitis, and cardiac failure; early clinical deterioration after initiation of feeds in malnutrition; sepsis (including in SAM); severe burns; major trauma; hypoxia; and unresponsive lactic acidosis. However, in the absence of specific diagnostic tests, the only way to diagnose TD is to carry out a therapeutic thiamine challenge. Considering its safety profile and wide dosage range, in such cases, thiamine can be administered by slow intravenous injection over 30 min. In severe acute conditions caused by TD, rapid clinical improvement will be seen (within hours or days) following thiamine administration.⁷

Thiamine deficiency global prevalence is poorly documented. Despite being easily treatable, TD continues to be seen in all age groups in both high and low resource countries with potentially severe and life-threatening consequences.⁷ Chittagong Medical College Hospital is the second largest tertiary level hospital in Bangladesh. It provides different specialist service mostly to the patients of south-eastern part of Bangladesh. It has a rich Neurology department. In our clinical practice we have encountered patients especially from Satkania, Bashkhali, Cox'sbazar, Teknaf, Saintmartin, Mosheshkhali upazillas of Chittagong Division with neurological features mimicking TD. Most of them are from low socio-economic strata. They are at risk of developing TD syndrome for their dietary habit. In our experience most of them show positive response to therapeutic trial of thiamine. However, there is paucity of any survey or systemic study in this issue. This situation has stimulated us to design this study to evaluate the clinico-epidemiological features of these patients and to assess their response to thiamine trial in a systematic way.

2. Research questions:

- What is the clinic-epidemiological profile of adult patients with suspected dry beriberi ?
- How do they response to therapeutic thiamine challenge?

3. Objectives:

3.1 General objective:

- To evaluate the efficacy of Thiamine in patients with suspected / possible dry beriberi

3.2 Specific objectives:

1. To describe the socio-demographic profile of patients
2. To categorize the patients according to their presenting symptoms and signs.
3. To assess and compare pre and post treatment neurological features

4. Rationale:

A vast population of southern area of Chittagong division of Bangladesh (Satkania, Bashkhaki, Cox'sbazar, Teknaf, Moheshkhali, Saint martin) are at risk of developing thiamine deficiency syndrome due to their dietary habit and low socio-economic condition. In our day to day clinical practice we have encountered many of them with neurological complaints mimicking thiamine deficiency (TD). However, TD has a large clinical spectrum, and as such it is frequently misdiagnosed, sometimes with fatal consequences or permanent neurological sequelae. TD can be investigated using plasma, erythrocytes, whole blood ThPP levels, and urinary excretion of thiamine before and after exogenous thiamine administration. But none of these investigations allow immediate diagnosis of TD in life-threatening conditions and they are rarely available in resource-limited settings. So, the diagnosis of TD in such contexts is a real challenge and a high level of clinical suspicion should be demonstrated in such situations. Early treatment with thiamine has the potential to rapidly reverse clinical signs and minimize sequelae, before the onset of fixed lesions. The lack of diagnostic capacity in our settings justifies the use of a therapeutic thiamine challenge in cases with high clinical suspicion. It is an effective, inexpensive, and easy to administer medication.

This issue of dry beriberi has got less attention and in our extensive literature search we have failed to identify any document related to dry beriberi in this part of Bangladesh. So, it is rational to design a prospective study to determine the clinical pattern of patients with suspected dry beriberi and their outcome to thiamine therapeutic challenge in our setting. Our study result is likely to sensitize the health professionals of this region about this neglected health issue by increasing awareness of the clinical spectrum of TD. Moreover, study may provide the impetus for fashioning national policies on the diagnosis, treatment and prevention of thiamine deficiency disorders in our country.

5. Metarials and methods:

5.1 Type of study: Quasi-experimental study, self –controlled clinical trial (pretest – posttest design)

5.2. Period of study: One year.

5.3. Place of study: Department of Neurology, Department of Medicine of Chittagong Medical College Hospital.

5.4. Study population: All the patients admitted in the above mentioned ward of CMCH with clinical diagnosis of suspected dry beriberi.

5.5. Sampling technique: Required number of patients will be selected purposively as per set criteria

5.6. Eligibility criteria:

Inclusion criteria:

1. Any person admitted to CMCH as a Suspected/Possible dry-beriberi.

Risk factors + at least 2 of the following signs:

Risk factors include Imbalanced diet (diet poor in thiamine/rich in carbohydrate or anti-thiamine factors), malnutrition, alcoholism, GIT surgery, chronic diarrhoea, chronic vomiting, pregnancy or history of recent delivery, chronic. diuretics use, renal dialysis, total parenteral nutrition.

- a) Muscle weakness of upper and or lower limb (less than grade 5 power in MRC scale)
- b) Positive sensory symptoms (burning, tingling or pain)
- c) Objective sensory deficit (pain, touch, position, vibration sense)
- d) Absent or reduced deep tendon reflexes
- e) Positive squat test (unable to rise after squatting without help)
- f) Leg swelling

2. Age 18 years and above

Exclusion criteria:

1. Patients with isolated cardiac/wet beriberi
2. Patient with known causes of peripheral neuropathy such as Diabetic, hereditary, Demyelinating (GBS, CIDP), metabolic (hepatic/renal impairment), drugs (e.g. INH, Ethambutol, Phenytoin, Metronidazole, Dapsone etc.) Toxin (As ,OPC, Pb ,Hg except alcohol) etc.
3. Patients refuse to participate

5.7. Sample size:

To estimate the prevalence following formula will be used to determine the sample size by doing finite population correction:

$$n = \frac{z^2 pqN}{d^2 \times (N - 1) + z^2 pq}$$

Where,

n= required sample size,

z= z-value of standard normal distribution at a given level of significance

p=prevalence of the event (Prevalence of clinically suspected dry beriberi patients show positive response to thiamine trial, usually from previous study)

q=100-p

d= allowable error/precision in the estimate of 'p'= usually 10% of p

N= Expected number of suspected dry-beriberi patients admitted in Neurology and Medicine department of CMCH during data collection period.

Here,

$z= 1.96$ at 95% confidence level

$p=80\% = 0.8$ [Prevalence of clinically suspected dry beriberi patients show positive response to thiamine trial is not available from extensive literature search. However, from our experience, 80% of these patients show positive response].

$q= (100-80)\% = 20\% = 0.2$

$d=10\% \text{ of } p = .1 \times .7 = .07$

$N= 75$

$$\text{So, } n = \frac{1.96^2 \times 0.8 \times 0.2 \times 75}{(.08)^2 \times (75-1) + 1.96^2 \times 0.8 \times 0.2} = 41.6 \approx 42$$

However, final sample size will be increased to 55 assuming 30% drop out.

5.8. Data collection tool:

- A predesigned Case Record Form.

5.9. Procedure of collecting data:

All patients attending the above mentioned ward with a diagnosis of suspected dry beriberi will be assessed for eligibility. Informed written consent will be obtained from the patients or attendants after full explanation of the ultimate outcome, complications and purpose of the study. They will be informed of their right to withdraw from the study at any stage. After consenting, the details of the patient's history including demographic information, food habit, clinical findings at presentation, results of laboratory, and neuroimaging testing will be recorded in case record form. A general physical examination (e.g. pulse, blood pressure, respiratory rate), neurological examination (higher mental function, cranial nerves, Motor, sensory, cerebellar function), results of laboratory and electro-diagnostic testing (if necessary) were recorded in case record form. Then therapeutic trial of Inj. Thiamine is given IV for 1st week (200mg IV daily) then orally (tab. Thiamin 100mg bd) for 12 weeks. Patients will be followed up after 1, 6 and 12 week to see the response.

5.10. Data analysis:

All the data will be checked and edited after collection. Continuous data will be reported as the means \pm SD or median and itraquartile range. Qualitative or categorical data will be described as frequencies and proportions. Proportions will be compared using chi-square or Fisher's exact test whichever will be applicable. To determine whether any of the difference between pretreatment and post treatment values were statistically significant or not, either Friedman's test or Cochran's Q test were used. Former test compares the quantitative variables and non-dichotomous qualitative variables and the later test compares the dichotomous qualitative/categorical variables. Statistical significance will be defined as $P < 0.05$ and confidence interval will be set at 95% level. SPSS (Statistical Package for Social Science) for Windows version 23 software will be used for the analyses.

5.11. Variables under study:

Primary Outcome Variable:

1. Treatment response measured by Overall Neuropathy Limitation Scale (ONLS) score before and after treatment.

Secondary Outcome Variables:

1. Comparison and Assessment of clinical features at presentation and after treatment: leg swelling, muscle cramp, muscle power (MRC grading), deep tendon reflexes, sensory impairments (tingling /burning /pain/ touch/ position /vibration), squat test.

5.12 Operational definition:

Risk factors: Imbalanced diet (diet poor in thiamine/rich in anti-thiamine factors), malnutrition, alcoholism, GIT surgery, chronic diarrhea, chronic vomiting ,pregnancy, diuretics, renal dialysis, total parenteral nutrition.

Anti-Thiamine factors: Raw or fermented fish,shell fish,ferns, Tea, coffee, betel nuts

Possible/suspected dry beriberi: Risk factors + at least 2 of the following signs:

- a) Muscle weakness of upper and or lower limb (less than grade 5 power in MRC scale)
- b) Positive sensory symptoms (burning, tingling or pain)
- c) Objective sensory deficit (pain, touch, position, vibration sense)
- d) Absent or reduced deep tendon reflexes
- e) Positive squat test (unable to rise after squatting without help)
- f) Leg swelling

Probable dry beriberi: Above symptoms recovered after thiamine treatment.

Socio-economic status: It will be measured as per Modified Kuppuswamy Socio-economic scale (Appendix-A) and grouped into five categories :Upper class, Upper middle class, Lower middle class, Upper lower class and Lower class.

5.14. Utilization of results:

This study result will be helpful to formulate a guideline for the management of suspected case of dry beriberi in our setting and improve the outcome of beriberi by reducing over or under treatment. Further research on such procedure can be designed by utilizing the results of this study.

6. Facilities:

Administrative setup and resource persons are available in the study site.

[figure not shown]
7. Approval of the head of the research cell and ERC:

Under consideration.

8. Clarification of the ethical issue:

1. Voluntary consent will be taken from each patient to be enrolled for the forthcoming study. patient's legal guardian will be approached where required.
2. All measures will be taken to preserve patients' anonymity and privacy. To do such, a separate case record form (CRF) will be utilized for every patient issuing a different identity code and only principal investigator will have access to patients' data. To be more, personal information of any of them will not be handed over any third party without their consent.
3. Evaluation of each research participant will be done thoroughly. Required investigations including radio-imaging and biochemical tests will be done in the CMCH if facilities available.
4. They will be treated as per treatment guideline for the disease of research interest. Importantly, no financial support will be provided to any research participant for being a subject in the research work.
5. All patients' will be informed about the nature and purpose of the study. They will get informed that their participation in the coming study research will not only benefit them but also the whole community as well.

5.13. Flow Chart of Study Design:

5.15 Time schedule:

	item	July to August 2018	September to October 2018	November 2018 to April 2019	May 2018	June 2019
1	Literature search & protocol writing					
2	Piloting & CRF(Case record form) Finalization					
3	Data collection					
4	Data entry					
5	Data analysis					
6	Report writing					
7	submission					

References:

1. WHO & UNHCR. 1999. Thiamine deficiency and its prevention and control in major emergencies. WHO/NHD/99. 13.

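### Section 5.7 reaches its 8-point precision only through a finite-population correction (N=75) that does not apply to the future patients the result is meant for; without it, 42 patients give about 12 points

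*Combined protocol and SAP*

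**What the plan says.** Section 5.7 (Sample size) is the only place where the protocol justifies its size. It treats the study as the estimation of one proportion, the share of suspected dry beriberi patients who respond to thiamine, and states that the "following formula will be used to determine the sample size by doing finite population correction". The population term is defined as "N= Expected number of suspected dry-beriberi patients admitted in Neurology and Medicine department of CMCH during data collection period" and set to 75. The other inputs are z = 1.96, p = 0.8 (from the investigators' experience, as no published figure was found) and an allowable error of 10% of p. The worked result is 41.6, taken as 42. The section ends: "However, final sample size will be increased to 55 assuming 30% drop out".

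The general objective in 3.1 is "To evaluate the efficacy of Thiamine in patients with suspected / possible dry beriberi". Section 5.14 says: "This study result will be helpful to formulate a guideline for the management of suspected case of dry beriberi in our setting". The rationale (section 4) also hopes to inform national policy.

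Section 5.10 says: "Qualitative or categorical data will be described as frequencies and proportions". It also says that the "confidence interval will be set at 95% level", but it names no interval for a response rate. The primary outcome in 5.11 is "Treatment response measured by Overall Neuropathy Limitation Scale (ONLS) score before and after treatment", with no cut-off that would make a patient a responder.

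**The concern.** A finite-population correction shrinks the standard error because part of a fixed, countable population has been observed. It is right when the conclusion is about that population and the sample is drawn from it at random. Here the fixed population would be the 75 or so patients admitted during data collection. An efficacy claim and a management guideline are about patients who come afterwards.

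A limiting case shows the problem. If all 75 were enrolled, the factor sqrt((75 − 75)/74) would be zero and the response rate would carry no uncertainty. The response rate in the next patients would still be uncertain.

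What is at stake is the plan's only sizing argument. A reader of 5.7 would expect a response rate about one and a half times as precise as 42 patients can give. Two further steps in the section, the value of the allowable error and the dropout allowance, also do not hold together.

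**Working it through.** **Inputs, all from section 5.7:** z = 1.96, p = 0.8, q = 0.2, N = 75, stated n = 42, 30% dropout, 55 enrolled. The allowable error d is printed as .07 in the input list (as .1 × .7), but .08 is used in the formula, which is what 10% of 0.8 gives.

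**1. The plan's own figure.** n = z²pqN / (d²(N − 1) + z²pq), with z²pq = 1.96² × 0.16 = 0.61466.
- d = 0.08: 46.099 / (0.0064 × 74 + 0.61466) = 46.099 / 1.08826 = 42.36. The plan prints 41.6. Both round to 42; strict rounding up of 42.36 gives 43.
- d = 0.07: 46.099 / (0.0049 × 74 + 0.61466) = 46.099 / 0.97726 = 47.17, which does not match the plan.

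So 42 comes from d = 0.08; the .07 and the 41.6 are slips.

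**2. Size without the correction.** n = z²pq / d² = 0.61466 / 0.0064 = 96.04, so 97 evaluable. The correction removes more than half of the requirement, and 97 exceeds the 75 admissions expected.

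**3. Precision.** The half-width is 1.96 × sqrt(0.16/n); the correction multiplies it by sqrt((75 − n)/74).

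| Evaluable n | Without correction | With correction |
|---|---|---|
| 38 | 12.7 points | 9.0 points |
| 42 | 12.1 points | 8.1 points |
| 55 | 10.6 points | 5.5 points |

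At n = 42 the ratio is 0.1210 / 0.0808 = 1.50.

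**4. Sensitivity to the interval method.** With 34 responders of 42 (81%), the exact interval is 65.9% to 91.4%, a half-width of about 12.8 points. The Wilson half-width is about 11.7 points. The conclusion does not depend on the method.

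**5. Dropout.** The 55 is 42 × 1.3 = 54.6. Losing 30% of 55 leaves 55 × 0.7 = 38.5, about 38 evaluable. Keeping 42 needs 42 / 0.7 = 60 enrolled. With 55 enrolled, 42 remain only if dropout is 1 − 42/55 = 23.6%.

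**The case against.** The strongest reply is that little depends on this. The planned analyses are Friedman and Cochran tests, the primary outcome is a before/after neuropathy score that 5.7 does not size, and no response-rate interval is named. That is correct, and it limits the finding to the stated justification and to any response-rate interval reported later.

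A second reply is that the correction matches the declared study population. Section 5.4 covers patients admitted to the named wards, some aims are descriptive, and the guideline is for the local setting. This shows where N came from, but it does not rescue the correction: even a guideline for this hospital alone governs later admissions. The documents do not mention future patients in so many words; the reading follows from the objective and the stated uses.

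Third, the contrast of 12.1 with 8.1 applies at n = 42, whereas the plan enrols 55. Over 38 to 55 evaluable patients the uncorrected half-width runs from 12.7 to 10.6 points. All of these miss the 8-point target.

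Fourth, the remaining slips are small. The .07 looks like a leftover, and falling from 42 to 38 evaluable adds only 0.6 points to the half-width. That is fair; they need correcting but do not carry the main point.

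Finally, purposive selection in 5.5 sits uneasily with 5.4 and 5.9, which speak of all patients, but it may mean only that the eligibility criteria are applied. It is therefore a secondary, conditional point. The main finding would stand under random sampling too.

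**Conclusion.** The concern holds. The 8-point precision in 5.7 depends entirely on a correction that does not suit the study's purpose. For the patients to whom the result will be applied, the nominal 95% half-width is 12.1 points at the plan's 42 patients, about 12.7 after the stated dropout from 55, and 10.6 if nobody drops out. The stated enrolment also does not deliver 42 evaluable patients at 30% dropout.

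These figures assume a true response rate of 80%, the normal approximation, and patients who can be treated as a random sample of future cases; the last is why they are nominal. They describe a response proportion only and say nothing about the adequacy of 55 patients for the before/after comparison. The text should be corrected, but the planned tests remain valid as far as this point goes.

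**What to change.** In 5.7, delete the finite-population correction with its inputs and worked result, keep 55 enrolled, and state:

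> With 55 enrolled and 30% dropout, about 38 patients will be evaluable, and a response proportion of 80% would be estimated with a nominal 95% half-width of about 13 points (10.6 points if all 55 are evaluable). No finite-population correction is used, and this figure does not size the ONLS comparison.

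Three additions belong with it:
- The actual reason for choosing 55. If it is feasibility, the 75 expected admissions can be cited for that purpose.
- One line defining a positive response, because 5.11 gives the score without a cut-off and 5.12 refers only to recovery.
- A statement that any reported response-rate interval is computed without the correction.

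As a secondary step, reword 5.5 so that consecutive eligible, consenting patients are enrolled until 55 is reached, and keep a simple log of eligible patients not enrolled.

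The cost is wording in 5.7 and 5.5, the response definition and interval statement, and the log. The stated precision becomes less favourable, about 13 points instead of 8. No patients or tests are added, and the Friedman and Cochran analyses do not change. Reaching 8 points is not a practical alternative, since the 97 evaluable patients it needs exceed the expected admissions.
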